## 1.0 Introduction

This Statistical Analysis Plan (SAP) provides describes the statistical analyses outlined and specified in the Protocol UB-313-101 Version 2.0: A First-in-Human Study to Evaluate the Safety, Tolerability, and Immunogenicity of UBITh® Migraine Immunotherapeutic Vaccine (UB-313) in Healthy Participants, dated 14 June 2022.

## 2.0 Study Objectives and Design

### 2.1 Objectives and Endpoints

The primary, secondary, and exploratory objectives and endpoints of this study are shown below.

**Table 1. Objectives and Endpoints**

Objectives	Endpoints
Primary Safety and Tolerability	
To evaluate the safety and tolerability of UB-313, when administered at selected dose regimens given intramuscularly (IM) to healthy adults.	Safety will be assessed by adverse events (AEs), adverse events of special interest (AESIs), medically attended adverse events (MAAEs), local (injection site) and systemic (generalized) reactions (i.e., reactogenicity), clinical laboratory assessments (e.g., chemistry, hematology, urinalysis), vital signs, neurological and physical examinations and electrocardiograms (ECGs), through the end of study.
Primary Immunogenicity	
To evaluate the anti-Calcitonin Gene-Related Peptide (anti-CGRP) specific antibody responses to selected UB-313 dose regimens in healthy adults.	Immunogenicity will be measured serum anti-CGRP antibody titers and analyzed from baseline to Week 16 and Week 44.
Secondary	
To evaluate the effects of selected UB-313 dose regimens on capsaicin-induced dermal blood flow (DBF) as a surrogate marker of target engagement.	Pharmacodynamics (PD) of the immune response will be measured by the inhibition of capsaicin-induced increase in DBF and will be analyzed from baseline to Week 16 and until return to baseline or until Week 44, whichever comes first.
Exploratory	
To evaluate the effects of selected UB-313 dose regimens on CGRP concentrations in serum.	CGRP concentrations in serum through the end of study.
To characterize antibodies generated by UB-313.	Antibody titers against components of the UB-313 (i.e., CpG1 and UBITh1) through the end of study. Isotype-specific anti-CGRP antibody titers through the end of study.

To examine cytokine release induced by UB-313.	Cytokine release from peripheral blood mononuclear cell (PBMC)s stimulated with component of the UB-313 (T-cell ELISpot) through Week 16.
--	---

[figure not shown]
## 2.2 Study Design

This is a single-site, randomized, double-blind, placebo-controlled, multi-dose regimen, first-in-human study of UB313, an anti-CGRP peptide-based immunotherapy candidate. Details for study design are described in protocol section 3.

The study design is shown in

Figure 1.

**Figure 1 Study Design Schematic**

\*No more than 4 participants will be dosed in a 24-hour period.

\*No more than 4 participants will be dosed in a 24-hour period.

Abbreviations: C (capsaicin Challenge); EoS (End of Study); EoT (End of Treatment); M (month); SCR (Screening Period); h (hour); Wk (week).

SRC (Safety Review Committee) is responsible for the safety review and dose escalation decision. At the end of Week 16, an EoT analysis will be performed for each cohort, unblinded by treatment cohort and pooled by dose on all safety, tolerability, immunogenicity and DBF data. At the end of the treatment analysis, study team members who are responsible for the conduct and data management of the study, and participants will remain blinded to the subject level treatment assignment. If there are no safety concerns, the study will continue until all participants complete Week 44 (End of Study [EoS]) visit. An unblinded statistics team from an external CRO (AvanSight) will perform the EOT and EOS analyses.

### **3.0 Analysis Sets**

The following populations sets will be used for the analyses.

- Full Analysis Set (FAS) consists of all participants randomized and received all three administrations of study Investigational Medicinal Product (IMP) per protocol, and who have at least one evaluable post baseline assessment of the anti-CGRP antibody titers.
- Safety Analysis Set (SS) consists of all participants who receive at least 1 dose of study IMP.

Demographic, baseline, and safety analysis will be based on Safety Analysis Set. Immunogenicity analyses, pharmacodynamics (PD) analyses, and exploratory analyses will be performed for FAS.

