Laser imaging and capsaicin challenge ⁴	X	X				X					X	X						X	X ¹⁶	X ¹⁶

Abbreviations: AE = adverse event; CRU = Clinical Research Unit; D = day; DBF = dermal blood flow; ECG = electrocardiogram; EoS = End of Study; EoT = End of Treatment; ET = Early Termination; FSH = follicle-stimulating hormone; H = hour; HBV = hepatitis B virus; HCV = hepatitis C virus; HIV = human immunodeficiency virus; IM = intramuscular; IMP = investigational medicinal product; LSCI = Laser Speckle Contrast Imaging; MRI = magnetic resonance imaging; PBMC = peripheral blood mononuclear cell; PD = pharmacodynamic; SAE = serious adverse event; SD = standard deviation; SRN = Screening; TC = telephone call; V = visit

1. The Investigator may perform visits outside of the scheduled study visits (unscheduled visits) listed in the table to conduct evaluations or assessments required to protect the well-being of the participant.
2. Screening and V1 visits can be rescheduled, and Screening window may be extended.
3. AEs/SAEs recording from time of informed consent up to and including Follow-up or ET.
4. On IMP administration days, all laboratory, PD, and capsaicin assessments are to be performed prior to IMP administration.
5. After each IMP administration, (a) participants will stay for 6 hours (± 2 hours) after injection for safety observation (except for sentinel participants who will stay for 24 hours after the first dose), (b) participants (except the sentinels' first dose) will have an approximately 24-hour onsite safety review including review of vital signs, temperature, diary, AEs, and medications, (c) all participants will have a telephone call approximately 48-hours post IMP injection for safety check including AE and medication review, and (d) all participants will complete a diary daily for 7 days, starting from the day of IMP administration.
6. On IMP administration days, vital signs (including temperature) will be measured before and after IMP administration.
7. Participants should be resting in a semi-recumbent position for at least 10 minutes before vital signs measurements. Semi-recumbent vital signs will include heart rate, systolic and diastolic blood pressure, respiratory rate, and body temperature.
8. Full neurological and physical examinations are to be performed during Screening, at Week 16 (EoT), Week 44 (EoS), and ET; brief (targeted) examinations may be performed at all other visits.
9. Laboratory assessments are detailed in Section 7.7 and Appendix 1.

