### **4.0 General Consideration**

All analyses will be conducted using observed data only and no missing data will be imputed.

In general, the baseline value is defined as the last available value before the first injection of study dose.

All analysis and summary will be performed by dose group, defined as below:

- 100/100/100 $\mu$ g (8 active participants in cohort 1)
- 300/100/100 $\mu$ g (8 active participants in cohort 2)

- 300/300/300 $\mu$ g (8 active participants in cohort 3)
- 600/100/100 $\mu$ g (8 active participants in cohort 4)
- Placebo (8 participants from all cohorts)

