#### 5.1.1 Immunogenicity Analyses

##### 5.1.1.1 Serum anti-CGRP Antibody Titers (Primary Endpoint and Analysis)

The primary immunogenicity endpoint is serum anti-CGRP antibody titers.

The anti-CGRP antibody titers and change from baseline will be summarized at each visit.

Comparison between each UB-313 groups and Placebo group in change from baseline will be based on an analysis of covariance (ANCOVA) model including dependent variable of change from baseline in titer values at each postbaseline visit, with factor of treatment, and baseline titer as covariate.

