#### **5.1.2 Pharmacodynamics (PD) Analyses**

##### **5.1.2.1 Capsaicin Induced Dermal Blood Flow (Secondary Endpoint and Analysis)**

###### Capsaicin-induced increase in DBF (CIDBF)

The pharmacodynamics (PD) endpoint is the inhibition of capsaicin-induced increase in DBF (CIDBF). The DBF at each timepoint at each visit will be calculated as the average of two capsaicin-induced locations.

The DBF will be summarized for each timepoint (i.e., 0, 15, 30, 45, and 60 minutes) at each visit (i.e., Day 1, Day 29, Day 57, Day 85, Day 113, and Day 141, Day 197, Day 253, Day 309 as applicable).

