#### 5.2.2 Treatment Tolerability

Overall treatment tolerability will be summarized in the safety population.

The overall treatment tolerability of UB-313 for each dose group is defined as the percentage of number of administered doses divided by number of administered doses plus number of missed doses of participant(s) who drops out due to drug-related AE(s). It is calculated according to the following formula:

$$100\% \times (A+B1+C+D) / (A+B1+B2+C+D)$$

where

A: number of administered doses of completers

B1: number of administered doses of participant(s) who drops out due to drug-related AE(s)

B2: number of missed doses of participant(s) who drops out due to drug-related AE(s)

C: number of administered doses of participant(s) who drops out due to drug-unrelated AE(s)

D: number of administered doses of participant(s) who drops out not due to AE(s)

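### The Full Analysis Set admits only participants given all three injections, so valid titers and blood-flow data from before injection 3 are discarded for anyone who later misses it

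*SAP*

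**What the plan says.** SAP section 3.0 defines two sets.

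- **FAS:** "Full Analysis Set (FAS) consists of all participants randomized and received all three administrations of study Investigational Medicinal Product (IMP) per protocol". At least one evaluable post-baseline anti-CGRP titer is also required.
- **Safety Set:** anyone given at least one dose. Its use is limited: "Demographic, baseline, and safety analysis will be based on Safety Analysis Set".

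The remaining analyses go to the FAS: "Immunogenicity analyses, pharmacodynamics (PD) analyses, and exploratory analyses will be performed for FAS". Section 5.1 repeats this. The primary model in section 5.1.1.1 takes as its "dependent variable of change from baseline in titer values at each postbaseline visit", so it is fitted at early visits as well as at Week 16. Section 4.0 adds: "All analyses will be conducted using observed data only and no missing data will be imputed". The only sensitivity analyses announced, in section 6.0, concern outliers.

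On timing, footnote 4 to the protocol's Table 1 says: "On IMP administration days, all laboratory, PD, and capsaicin assessments are to be performed prior to IMP administration". SAP section 5.1.2.1 lists the DBF visits as "Day 1, Day 29, Day 57, Day 85, Day 113, and Day 141, Day 197, Day 253, Day 309 as applicable".

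**The concern.** A set named Full normally keeps close to everyone randomised. This one selects on an event up to 12 weeks after randomisation. Whether a Day 29 titer counts depends on whether an injection is given on Day 85, although that injection cannot have influenced the Day 29 value. At the visits before injection 3 the restriction gains nothing scientifically. It removes collected data and introduces selection.

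Other parts of the SAP allow for participants whom this set would drop. The tolerability formula in section 5.2.2 has a term for doses missed by participants who leave because of drug-related adverse events. The AUC rule in section 5.1.1.4 uses an early dropout's titers up to the last available visit, but under this FAS it can apply only to people who leave after injection 3.

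If stopping is related to reactogenicity or immune response, then titers, responder rates and DBF effects describe only those who received the full regimen, and the selection can differ between dose groups. The eight placebo participants serve all four comparisons, so one placebo exclusion touches every contrast. The protocol synopsis says the Week 16 read-out is meant to refine the development plan, so it matters which population the estimates describe.

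**Working it through.** The documents contain no dropout rate and no power calculation, so there is no figure to reproduce. The check counts visits and then shows the effect under stated assumptions.

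**1. Visits before injection 3 (Day 85)**
- Titers (antibody row of the protocol's Table 1): post-baseline Days 8, 29, 36, 57, 85, 113, 141, 197, 253 and 309, which is 10 visits. Day 85 is sampled before dosing, so 5 of 10 precede injection 3 (5 of the 6 up to Week 16).
- DBF (SAP section 5.1.2.1): post-baseline Days 29, 57, 85, 113, 141, 197, 253 and 309, which is 8 visits. Days 29, 57 and 85 precede injection 3: 3 of 8 (3 of the 4 up to Week 16).

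Someone who attends through Day 85 and misses only injection 3 therefore has 5 titers and 3 DBF visits in the database, and none in the analysis.

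**2. How likely an exclusion is.** Group size is 8 (SAP section 4.0). With an assumed chance q of not receiving all three injections, P(at least one of 8 excluded) = 1 − (1 − q)^8.

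| Assumed q | P(at least 1 of 8) | Expected exclusions of 40 |
|---|---|---|
| 5% | 33.7% | 2 |
| 10% | 57.0% | 4 |
| 15% | 72.8% | 6 |
| 20% | 83.2% | 8 |

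**3. Values discarded per dose group**
- Planned titers before injection 3: 8 × 5 = 40. One stopper loses up to 5 (12.5%), two lose up to 10 (25%).
- Planned DBF visits before injection 3: 8 × 3 = 24. One stopper loses up to 3, two lose up to 6.

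**4. Precision at visits the stoppers attended** (common SD, baseline covariate ignored)
- Against placebo, 7 v 8: √(1/7 + 1/8) / √(1/8 + 1/8) = 1.035, so the SE rises 3.5%.
- Against placebo, 6 v 8: √(1/6 + 1/8) / √(1/8 + 1/8) = 1.080, so it rises 8.0%.
- Single-group mean: √(8/7) = 1.069 and √(8/6) = 1.155, so 6.9% and 15.5%.

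**5. Shift in geometric mean titer at attended visits.** If k of 8 are excluded and their titers differ f-fold from the rest, the mean of those retained differs from the mean of all 8 by a factor f^(k/8). It moves up if stoppers are lower and down if they are higher.

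| Assumed f | k = 1 | k = 2 |
|---|---|---|
| 2 | 1.09 | 1.19 |
| 4 | 1.19 | 1.41 |
| 10 | 1.33 | 1.78 |

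**6. Responder rate, an extreme case.** Suppose two stoppers are non-responders and the other six respond. At any visit the stoppers attended, the plan reports 6/6 (Clopper-Pearson 95% CI 54% to 100%) where the observed data give 6/8 (35% to 97%).

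**The case against.** The strongest reply concerns the primary time points. The protocol synopsis places them at the end of Week 16 and in the maintenance period to Week 44, both after injection 3. The visits certain to be affected are analysed but are not those time points. With observed data only, a stopper who leaves the study contributes nothing at Week 16 under either definition. A stopper who stays adds a partly dosed participant to the regimen group, which answers a different question. In an unpowered first-in-human study whose objective refers to selected dose regimens, leading with the full-regimen population can be defended.

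Much of this stands as a limit on size. The Week 16 result changes only if stoppers remain in follow-up. The supplied text does not say whether they will, although SAP section 5.3.1.1 tabulates treatment discontinuation separately from study discontinuation. The dropout rates and fold differences above are assumptions. The tolerability formula shows that drug-related missed doses are allowed for, not that they are expected or differ by regimen. Section 5.3.1.1 also plans to count each analysis set and list exclusions, so the loss would be visible.

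None of this supports making the restricted set the only one. The primary model is fitted at every post-baseline visit, half of the titer visits precede injection 3, and listing exclusions does not put the data back. The supplied protocol text has no analysis-set section, so agreement with the protocol could not be checked. The SAP's contents list shows no other section where a wider set might sit.

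**Conclusion.** The concern holds and should be fixed. As written, the plan excludes from every immunogenicity and pharmacodynamic analysis anyone who misses an injection, and so discards up to 5 titer visits and 3 DBF visits that a participant may complete before missing the third. Missing injection 2 has the same consequence. Because section 3.0 does not define what receipt per protocol means, the set might also exclude people given all three injections with a deviation.

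Confidence is high on the wording and the visit counts. The bias is of unknown size and direction, and is zero if everyone receives three injections or if stopping is unrelated to response. With one or two stoppers of 8, the loss of precision at attended visits is modest (SE against placebo up 3.5% or 8.0%). The possible shift in geometric mean titer is larger, 1.09- to 1.78-fold over the assumed range. The co-primary safety analysis is not affected.

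**What to change.** In SAP section 3.0:

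- Define the FAS as all randomised participants with at least one injection and at least one post-baseline titer, analysed as randomised, using every observed visit. For the pharmacodynamic analyses, require at least one post-baseline laser speckle (LSCI) assessment in place of the titer.
- Rename the present three-injection set Per-Protocol, say what per protocol means, and keep it as a supportive analysis. The full-regimen question is still answered.
- Report the number excluded from the Per-Protocol set by dose group, building on the counts and listing already planned in section 5.3.1.1.

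If any first-phase analysis has already been run, date the change and report both sets. The cost is SAP wording and one extra set of tables, with no new participants or measurements. The benefit arises only if someone misses an injection: it comes first at the visits before injection 3, and extends to Week 16 and later only for stoppers who stay in follow-up.

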### **4.0 General Consideration**

All analyses will be conducted using observed data only and no missing data will be imputed.

In general, the baseline value is defined as the last available value before the first injection of study dose.

All analysis and summary will be performed by dose group, defined as below:

- 100/100/100 $\mu$ g (8 active participants in cohort 1)
- 300/100/100 $\mu$ g (8 active participants in cohort 2)

- 300/300/300 $\mu$ g (8 active participants in cohort 3)
- 600/100/100 $\mu$ g (8 active participants in cohort 4)
- Placebo (8 participants from all cohorts)

## 5.0 Statistical Analyses

### 5.1 Immunogenicity, Pharmacodynamics, and Exploratory Analyses

Efficacy analysis will be based on FAS. All analyses and plot will be performed by dose group for each visit and each timepoint unless otherwise specified. In general, summary of a variable (e.g., titer, CIDBF) will include baseline, actual value, and change (or percent change) from baseline when applicable. Summary plots will be done when applicable.

For qualitative assessments (e.g., titer value, CIDBF...), the distribution will be examined. If the distribution is similar to log normal, log transformation will be applied. In this case, geometric mean and GMR (Geometric Mean Ratio) will be presented in place of mean and difference. For model analysis, log transformed value will be used, analysis results will be presented after anti log transformation.

#### 5.1.1 Immunogenicity Analyses

##### 5.1.1.1 Serum anti-CGRP Antibody Titers (Primary Endpoint and Analysis)

The primary immunogenicity endpoint is serum anti-CGRP antibody titers.

The anti-CGRP antibody titers and change from baseline will be summarized at each visit.

Comparison between each UB-313 groups and Placebo group in change from baseline will be based on an analysis of covariance (ANCOVA) model including dependent variable of change from baseline in titer values at each postbaseline visit, with factor of treatment, and baseline titer as covariate.

### 5.1.1.2      **Serum anti-CGRP Antibody Titers vs Age and Gender (Exploratory)**

Relationship between immunogenicity and age, and gender differences in immunogenicity will be explored.

Serum anti-CGRP antibody titers will be summarized by gender.

### 5.1.1.3      **Seroconversion and Responder Rate (Exploratory)**

Additional exploratory endpoints are seroconversion status and sero responder status for each participant.

Seroconversion is defined as the ratio (i.e., geometric mean fold change) of post baseline titer over baseline titer  $\geq X$  (e.g., X=1, 2, 3, 4).

Seroconversion rates will be calculated for all postbaseline visits along with 95% CIs based on Binomial distribution. In addition, the difference in the response rates between UB-313 and the placebo group (UB-313 – placebo) will be calculated, and the 95% CIs based on Fisher's Exact test will be displayed.

To define the threshold of response, mean and standard deviation of titer values will be calculated using the assessments below.

- Titer values at baseline from all participants
- and
- Titer values at all postbaseline visits up to Week 16 from placebo participants.

The mean plus two standard deviations (mean+2SD) will be used as the threshold of response. Responders will be defined as the participants with titer value greater than or equal to response threshold for each visit including baseline and postbaseline visits.

Responder analysis will be done similarly to seroconversion rates.

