Statistical Considerations	
As this is an FIH study, the sample size is based on the exploratory nature of the design. No statistical power to be considered to determine the sample size.
 
Primary time-points for immunogenicity and PD are two-fold:
 
a) First phase at the end of Week 16 for evaluating maximal immuno-responses elicited by the 4 dosage regimens (i.e., cohorts) of UB-313
 
b) Second phase of response maintenance period after Week 16 until the end of study (Week 44), in which effects of the 4 dosage regimens of UB-313 on the duration of responses will be evaluated.
 
When any cohort completes Week 16, first phase analyses can be conducted based on cleaned cohort data up to Week 16. To maintain blinding for the remainder of the study, the first phase analyses will be conducted and reviewed only by a designated and independent team before the end of study final database lock. The purpose of the early analyses of first phase data prior to the completion of the study is to have an early read out of the first part of the primary immunogenicity and PD results to refine the development plan. Design of the second phase of the study will not be changed based on results from the first phase data.

Table 1: Study Schedule of Assessments

The Investigator may perform visits outside of the scheduled study visits (unscheduled visits) listed in the Schedule of Assessments table to conduct evaluations or assessments required to protect the well-being of the participant.

Visit Number ¹	Screen ²	V1 ^{2,5}		V1a ⁵	V1b ⁵	V2	V3 ⁵		V3a ⁵	V3b ⁵	V4	V5	V6 ⁵		V6a ⁵	V6b ⁵	V7	V8	V9, V10, V11	V12/ET
Week	Up to 4 wks	W0				W1	W4				W5	W8	W12				W13	W16	W20, W28, W36	W44
Day (Visit Window)	-28 to -1	D1 (-3D)	D1 --	D2	D3	D8 ($\pm 3D$)	D29 (-3D)	D29 ($\pm 3D$)	D30	D31	D36 ($\pm 3D$)	D57 ($\pm 5D$)	D85 (-3D)	D85 ($\pm 3D$)	D86	D87	D92 ($\pm 3D$)	D113 ($\pm 7D$)	D141, D197, D253 ($\pm 14D$)	D309 ($\pm 14D$)
Visit Type	SRN	Pre IMP	IMP	CRU	TC	CRU	Pre IMP	IMP	CRU	TC	CRU	CRU	Pre IMP	IMP	CRU	TC	CRU	EoT CRU	CRU	EoS/ET CRU
General Assessments and Procedures																				
Informed consent	X																			
Demographic	X																			
Medical history	X																			
Eligibility assessment	X	X																		
Medication review	X	X	X	X	X	X	X	X	X	X	X	X	X	X	X	X	X	X	X	
AE/SAE review ³	X	X	X	X	X	X	X	X	X	X	X	X	X	X	X	X	X	X	X	
Investigational Medicinal Product Administration and Assessments																				
Randomization		X																		

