IMP Injection ¹⁸			X					X								X				
Solicited local and systemic reactions assessment			X					X							X					
Extended unit stay ⁵			X ⁵					X							X					
Diary review ¹⁰			X	X		X		X	X		X				X	X		X		
General Safety Assessments																				
Vital signs (pre- and post-IMP) ^{6,7}	X		X	X		X		X	X		X	X		X	X		X	X	X	X
Height	X																			

Visit Number ¹	Screen ²	V1 ^{2,5}		V1a ⁵	V1b ⁵	V2	V3 ⁵		V3a ⁵	V3b ⁵	V4	V5	V6 ⁵		V6a ⁵	V6b ⁵	V7	V8	V9, V10, V11	V12/ET
Week	Up to 4 wks	W0				W1	W4				W5	W8	W12				W13	W16	W20, W28, W36	W44
Day (Visit Window)	-28 to - 1	D1 (-3D)	D1 --	D2	D3	D8 (±3D)	D29 (-3D)	D29 (±3D)	D30	D31	D36 (±3D)	D57 (±5D)	D85 (-3D)	D85 (±3D)	D86	D87	D92 (±3D)	D113 (±7D)	D141, D197, D253 (±14D)	D309 (±14D)
Visit Type	SRN	Pre IMP	IMP	CRU	TC	CRU	Pre IMP	IMP	CRU	TC	CRU	CRU	Pre IMP	IMP	CRU	TC	CRU	EoT CRU	CRU	EoS/ET CRU
Weight	X		X					X						X				X	X	X
Physical exam ^{4,8}	X		X					X						X				X		X
Neurological exam ^{4,8}	X		X					X						X				X		X
TriPLICATE ECGs ⁴	X		X			X		X			X			X				X	X	X
MRI ¹⁷	X																			
Laboratory Assessments ^{4,9}																				
HIV, HCV, HBV	X																			
Coagulation	X																			
Clinical chemistry ⁴	X	X				X	X				X	X	X					X	X	X
Hematology ⁴	X	X				X	X				X	X	X					X	X	X
Urinalysis ⁴	X	X				X						X						X		X
Urine drug screen ⁴	X	X				X						X								
Pre-IMP alcohol breath test ⁴	X		X					X									X			
Pre-IMP pregnancy test ^{4,11}	X		X					X									X			
FSH ¹¹	X																			
Inflammatory markers ^{4,12}	X	X				X						X						X		X
Cytokine panel (pre- and post- IMP) ¹³		X	X			X	X					X	X							
Pharmacodynamic Assessments ⁴																				
Serum antibodies ^{4,14}		X				X	X				X	X	X					X	X	X
Serum CGRP ⁴		X				X	X				X	X	X					X	X	X

Visit Number ¹	Screen ²	V1 ^{2,5}		V1a ⁵	V1b ⁵	V2	V3 ⁵		V3a ⁵	V3b ⁵	V4	V5	V6 ⁵		V6a ⁵	V6b ⁵	V7	V8	V9, V10, V11	V12/ET
Week	Up to 4 wks	W0				W1	W4				W5	W8	W12				W13	W16	W20, W28, W36	W44
Day (Visit Window)	-28 to -1	D1 (-3D)	D1 --	D2	D3	D8 ($\pm 3D$)	D29 (-3D)	D29 ($\pm 3D$)	D30	D31	D36 ($\pm 3D$)	D57 ($\pm 5D$)	D85 (-3D)	D85 ($\pm 3D$)	D86	D87	D92 ($\pm 3D$)	D113 ($\pm 7D$)	D141, D197, D253 ($\pm 14D$)	D309 ($\pm 14D$)
Visit Type	SRN	Pre IMP	IMP	CRU	TC	CRU	Pre IMP	IMP	CRU	TC	CRU	CRU	Pre IMP	IMP	CRU	TC	CRU	EoT CRU	CRU	EoS/ET CRU
PBMC for ELISpot ⁴		X																X		
Blood collection for research sample ^{4,15}		X				X	X				X	X	X				X	X	X	X
HLA typing (optional)																			X ¹⁹	X ¹⁹

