#### **5.1.2.4 Inhibition Responder (Exploratory)**

CIDBF at 30 minutes post capsaicin will be used for the responder analysis. To define threshold of response, mean and standard deviation will be calculated using the assessments below.

- CIDBF at baseline from all participants

The mean minus two standard deviations (mean-2SD) will be used as the threshold of response. CIDBF responders will be defined as the participants with CIDBF less than or equal to response threshold for each visit including baseline and postbaseline visits.

Responder analysis will be done similarly to seroconversion rates.

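### The seroconversion cut-off X=1 counts an unchanged titer as seroconversion, and the 95% CI for the rate difference is tied to a test that does not define one

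*SAP*

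**What the plan says.** SAP section 5.1.1.3 sets a status for each participant: "Seroconversion is defined as the ratio (i.e., geometric mean fold change) of post baseline titer over baseline titer" being at least X. The values 1, 2, 3 and 4 are given as examples, and the inequality is not strict. "Seroconversion rates will be calculated for all postbaseline visits", with binomial 95% CIs for each group.

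For the comparison with placebo, the quantity is "the difference in the response rates between UB-313 and the placebo group" (UB-313 minus placebo), and "the 95% CIs based on Fisher's Exact test will be displayed".

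The sero-responder rates at the end of section 5.1.1.3 follow the same method. So do the capsaicin-induced dermal blood flow (CIDBF) inhibition responders in section 5.1.2.4: "Responder analysis will be done similarly to seroconversion rates". Each dose group has 8 active participants, and the comparator is "Placebo (8 participants from all cohorts)" (SAP section 4.0). The protocol synopsis says of the design: "No statistical power to be considered to determine the sample size".

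**The concern.** There are two separate faults.

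**The cut-off.** A ratio of exactly 1 means no change, and it satisfies a rule of at least 1. The label then covers people with no immune response, so the placebo rate rises and the difference from placebo shrinks. The cut-offs 2, 3 and 4 do not count an unchanged titer.

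**The interval.** Fisher's exact test conditions on both margins of the 2×2 table. It yields a p-value and, by inversion, an interval for the odds ratio. It does not yield a unique interval for a difference in rates. The sponsor may intend some exact interval for the difference, but none is named. The method would therefore be chosen at programming, for three sets of comparisons: seroconversion, sero-responders and CIDBF responders. The single-group binomial CIs are not affected.

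**Working it through.** The plan gives no seroconversion rate, power or interval limits, so there is no figure to reproduce.

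**Inputs from the documents:** 8 per dose group and 8 pooled placebo (SAP 4.0); the rule ratio ≥ X (SAP 5.1.1.3); 10 post-baseline antibody visits, at Weeks 1, 4, 5, 8, 12, 16, 20, 28, 36 and 44 (Protocol Table 1).

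**Assumptions:** the documents give no dilution scale or assay variability, so a range is shown. Placebo has no true change and UB-313 is 8/8. The discrete model takes a two-fold dilution scale, with the log2 true titer uniform within a step. Independent normal error (SD in log2 units) is added at baseline and post-baseline, and each value is rounded to the nearest step (1,000,000 draws). The continuous model has symmetric error.

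**Step 1: no assumption needed.** Unchanged titer: ratio = 1 ≥ 1, so it counts. If all placebo titers are unchanged and all UB-313 titers rise, the difference is 8/8 − 8/8 = 0.

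**Step 2: effect of the cut-off.** Against 8/8, both the Newcombe and the exact unconditional interval exclude zero when placebo is 4/8 or fewer. At 8/8 vs 5/8 they are −0.027 to 0.694 and −0.05 to 0.755. The chance of excluding zero is therefore P(Bin(8, p) ≤ 4), where p is the placebo rate. For p = 0.50 this is (1+8+28+56+70)/256 = 163/256 = 0.637.

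| Titer model | Placebo rate, X=1 | Expected difference (1 − p) | P(zero excluded), X=1 | Placebo rate, X=2 | P(zero excluded), X=2 |
|---|---|---|---|---|---|
| Continuous | 0.50 | 0.50 | 0.64 | not computed | not computed |
| Two-fold, SD 1 | 0.635 | 0.365 | 0.33 | 0.365 | 0.88 |
| Two-fold, SD 0.5 | 0.743 | 0.257 | 0.12 | 0.257 | 0.97 |
| Two-fold, SD 0.25 | 0.859 | 0.141 | 0.02 | 0.141 | 0.998 |
| Two-fold, SD 0 | 1.000 | 0 | 0 | 0 | 1.0 |

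**Step 3: effect of the interval.** There are 8+7+…+1 = 36 tables with 8 per arm and more events on UB-313. Zero is excluded in:

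- 10 by Fisher p < 0.05;
- 12 by exact unconditional limits (score statistic, two one-sided 2.5% tests, maximised over the nuisance rate);
- 15 by Newcombe.

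The three agree in 31 tables. The 5 disagreements all have a difference of 4/8:

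| UB-313 vs placebo | Fisher p | Exact unconditional excludes 0 | Newcombe excludes 0 |
|---|---|---|---|
| 4/8 vs 0/8 | 0.077 | yes | yes |
| 5/8 vs 1/8 | 0.119 | no | yes |
| 6/8 vs 2/8 | 0.132 | no | yes |
| 7/8 vs 3/8 | 0.119 | no | yes |
| 8/8 vs 4/8 | 0.077 | yes | yes |

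Worked case, 6/8 vs 2/8 (difference 0.50):

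- Fisher: 2 × (784 + 64 + 1)/12870 = 0.132.
- Newcombe: the Wilson limits are 0.409 to 0.929 and 0.071 to 0.591. The lower limit is 0.50 − √[(0.75−0.409)² + (0.591−0.25)²] = 0.018, and the upper limit is 0.752.
- Exact unconditional: −0.05 to 0.85.
- Interval from inverting the conditional test: 0.65 to 148, on the odds-ratio scale.

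At 8/8 vs 4/8, Fisher p = 2 × 70/1820 = 0.077, yet Newcombe (0.07 to 0.78) and exact unconditional (0.06 to 0.84) both exclude zero.

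**The case against.** The best defence is that little depends on this. X=1 is offered as an example next to three sound cut-offs, and a reader who sees all four is unlikely to be misled. Read plainly, it gives the share of participants not below baseline, which has some descriptive use in the maintenance phase. The section is exploratory, there is no decision rule, and the protocol disclaims power. All of that stands, and it is why the point is minor. It does not make an unchanged titer a seroconversion, and an open list of examples leaves X=1 available for reporting.

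The percentages come from assumed models. That also stands. With a continuous titer, exact ties practically vanish and X=1 becomes a low threshold that half of untreated participants pass by chance. The 8/8 against 8/8 case needs every placebo titer to be exactly unchanged.

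Dropping X=1 does not make the remaining cut-offs free of noise. On a two-fold scale with SD 1, X=2 still gives a placebo rate of 0.365, and X=3 and X=4 select the same participants because a ratio of 3 cannot occur. This is fair, and the documents do not say which scale applies.

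On the interval, the estimand is clearly a difference, so an odds-ratio interval would probably not be displayed as one, and naming any sound method would close the gap. That is right: the exact unconditional interval is one acceptable choice among several. The gap itself remains, since no method is named.

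The 8-against-8 tables are also the largest possible. The FAS requires all three injections and at least one evaluable post-baseline titer (SAP section 3.0), and only observed data are used (section 4.0), so denominators may be smaller.

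**Conclusion.** Both parts hold, at minor severity. That X=1 counts an unchanged titer follows from the text alone. How far this dilutes the comparison depends on the assay: the assumed models give a placebo rate of 50% to 100%, and at best a 0.64 chance that the interval excludes zero even when UB-313 is 8/8. The interval point is secondary and closer to missing detail. It alters the reading of zero only in borderline tables, 5 of 36 at full enrolment. The primary titer ANCOVA (SAP 5.1.1.1) and the secondary CIDBF ANCOVAs (SAP 5.1.2.1) are not affected.

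**What to change.** 1. In SAP section 5.1.1.3, delete X=1 and replace the open list with a commitment to report X = 2, 3 and 4 at every post-baseline visit.
2. For all three rate comparisons (seroconversion, sero-responders, CIDBF responders), name one interval for the difference. A suitable choice is exact unconditional 95% limits that invert the score statistic with two one-sided 2.5% tests. Newcombe would also settle the matter if it is named in advance.
3. Keep Fisher's exact test for p-values only. With exact unconditional limits, add a footnote that the p-value and the interval can disagree (4/8 vs 0/8 and 8/8 vs 4/8).

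The cost is SAP wording and a standard software option, with no change to data collection. Dropping X=1 removes 10 visits × 4 dose groups = 40 comparisons with placebo. The exact unconditional limits are wider than Newcombe's (at 6/8 vs 2/8, about 0.90 against 0.73) and exclude zero in 12 rather than 15 of the 36 tables.
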